10.6.2.1. Marked Elevations in Serum Creatinine

For increases of SCr >50% relative to the participant baseline:

- Temporarily withhold IMP until a repeat SCr as soon as practically feasible, preferably within 24 hours of awareness.
- If the second measurement of SCr is still ≥50% from the participant baseline, IMP should be permanently discontinued.
- Adequate, immediate, supportive measures should be taken if AKI is suspected.

Version 3.0: 25 May 2022

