In the case of an SAE occurring during active treatment, the investigator will contact the medical monitor and notify the sponsor of the event as soon as possible. Dosing will be paused for all participants, until causality is assessed by the investigator and the sponsor. If the SAE is determined (by SRT) to be either drug-related or relationship is unknown, dosing at the current dose level will be stopped, and further dose escalation will be terminated. If the SAE is determined to be not drug-related by the investigator and the sponsor, then the trial may resume at the current dose level.

In addition, the dose escalation will be terminated based on the following PK criteria:

- MAD: If, based on the observed data, the group mean steady state (Day 14) C_{max} or AUC₂₄ (based on total plasma concentrations) of the next planned dose is projected to exceed the maximum exposures in SAD (Part A), that dose will not be explored. Modified doses may be explored if they are not expected to exceed PK stopping criteria.

Progression to the next dose will occur if the last dose was tolerated and after satisfactory review of the available safety, tolerability, and PK data from a minimum of 6 participants (including at least 1 placebo participant) within a treatment period.

The dose increments will be based on observed exposures and forward predictions. The size of the exposure increments may be changed (not exceeding 3.3-fold [half-log] increments) as the trial progresses, dependent upon emerging PK, safety, and tolerability data. Any decision to change the size of the exposure increment will be made jointly by the investigator and the trial team and after careful evaluation of all available data.

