6.6. Dose Modification

Guidance for dose escalation/stopping rules is provided in Section 4.4.

The decision to proceed to the next dose level of CVL-354 in successive cohorts/periods will be made by the SRT based on a full review of the safety, tolerability, and preliminary PK data obtained from the completed prior doses.

If ongoing data surveillance during the treatment interval reveals consistent notable AEs or safety concerns at a dose, which are determined to be attributable to the drug treatment, continued dosing within the cohort will be temporarily halted and no participants will be dosed until full safety review can take place to determine if dose modification or termination of the cohort are appropriate.

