10.3.2. Definition of SAE

If an event is not an AE per definition above, then it cannot be an SAE even if serious conditions are met (eg, hospitalization for signs/symptoms of the disease under trial, death due to progression of disease).

Table 15: Definition of SAE

An SAE is defined as any untoward medical occurrence that, at any dose in the view of either the investigator or sponsor, results in any of the following outcomes:

a. Results in death

b. Is life-threatening

The term "life-threatening" in the definition of "serious" refers to an event in which the participant was at risk of death at the time of the event. It does not refer to an event, which hypothetically might have caused death, if it were more severe.

c. Requires inpatient hospitalization or prolongation of existing hospitalization

In general, hospitalization signifies that the participant has been detained (usually involving at least an overnight stay) at the hospital or emergency ward for observation and/or treatment that would not have been appropriate in the physician's office or outpatient setting. Complications that occur during hospitalization are AEs. If a

complication prolongs hospitalization or fulfills any other serious criteria, the event is serious. When in doubt as to whether "hospitalization" occurred or was necessary, the AE should be considered serious.

Hospitalization for elective treatment of a pre-existing condition that did not worsen from baseline is not considered an AE.

d. Results in persistent disability/incapacity

The term disability means a substantial disruption of a person's ability to conduct normal life functions.

This definition is not intended to include experiences of relatively minor medical significance such as uncomplicated headache, nausea, vomiting, diarrhea, influenza, and accidental trauma (eg, sprained ankle) which may interfere with or prevent everyday life functions but do not constitute a substantial disruption.

e. Is a congenital anomaly/birth defect

f. Other situations:

Medical or scientific judgment should be exercised in deciding whether SAE reporting is appropriate in other situations such as important medical events that may not be immediately life-threatening or result in death or hospitalization but may jeopardize the participant or may require medical or surgical intervention to prevent one of the other outcomes listed in the above definition. These events should usually be considered serious.

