10.6.2. Potential Cases of Acute Kidney Injury

Abnormal values in SCr that meet the KDIGO 2012 (KDIGO, 2012) criteria below, in the absence of other causes of kidney injury, are considered potential cases of acute kidney injury (AKI) and should be regarded as important medical events.

- Increase in SCr ≥0.3 mg/dL (26.5 mmol/L) within 48 hours
- Increase in SCr ≥50% from baseline
- Urine volume output <0.5 mL/kg/h for 6 hours

The baseline is defined as the most recent SCr prior to randomization/dosing.

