10.6.2.2. Evaluation of Potential Cases of AKI

Participants suspected of having potential AKI should promptly (as soon as practically feasible, preferably within 24 hours of awareness) have an evaluation, which includes a detailed medical history, physical examination, and laboratory tests.

Laboratory tests include, at a minimum:

- Serum:
 - BUN, creatinine, sodium, potassium, chloride, bicarbonate, phosphorus, and calcium
 - Creatine kinase and cystatin-C
- Urine: Dipstick, microscopic examination, indices, and β-2-microglobulin.

Consider consultation with a nephrologist.

Close daily observation of the participant and assessment of kidney function should be continued until the SCr elevations and the associated abnormal UA results return to baseline or normalize.

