10.6.2.3. Stopping Criteria for the Cohort

Further dosing with IMP will be stopped for the cohort if ≥ 2 healthy participants within a given dose level meet the criteria established in Section 10.6.2.1 and permanently discontinued IMP.

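### Protocol 10.6.2.1 starts the creatinine hold above 50% but confirms at 50% or more, so a rise that stays at exactly 50% misses the hold, the discontinuation and the cohort count

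*Protocol*

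**What the plan says.** Appendix 6 of the protocol (Section 10.6) sets the kidney safety rules. Four steps use a creatinine rise of 50%, directly or by reference:

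- **Definition (10.6.2).** A potential AKI case, absent another cause of kidney injury, includes "Increase in SCr ≥50% from baseline". Such cases are to be treated as important medical events.
- **Hold (10.6.2.1).** The actions apply "For increases of SCr >50% relative to the participant baseline". The first is to withhold IMP until creatinine is repeated, preferably within 24 hours.
- **Confirmation (10.6.2.1).** "If the second measurement of SCr is still ≥50% from the participant baseline, IMP should be permanently discontinued".
- **Cohort stop (10.6.2.3).** Dosing stops for the cohort when at least two participants at a dose level "meet the criteria established in Section 10.6.2.1 and permanently discontinued IMP".

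The SAP does not restate these rules, so the protocol text is the only source.

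**The concern.** The definition and the confirmation include 50%; the hold trigger excludes it. The word *still* in the confirmation step implies that the first value was already at that threshold, which points to a slip in the trigger. If a stricter threshold for marked elevations had been intended, the confirmation should be strict too. As written, exactly 50% is enough to end treatment on the repeat but not enough to pause it on the first reading.

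This rule decides whether a participant in a first-in-human trial receives the next dose, and it feeds a cohort stop. For the same confirmed value of 50%, the outcome depends only on whether the first reading was slightly higher.

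**Working it through.** The plan gives no figure to reproduce. The check applies the rule as worded, then with the trigger set to ≥50%.

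**1. Apply the rule.** Rise = (reading − baseline) / baseline. Values are in mg/dL and are illustrative.

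| Baseline, first, second | Rises | Trigger >50% (as written) | Trigger ≥50% |
|---|---|---|---|
| 0.8, 1.2, 1.2 | 50%, 50% | no hold, no discontinuation, not counted | hold, discontinue, counted |
| 0.8, 1.3, 1.2 | 62.5%, 50% | hold, discontinue, counted | same |
| 0.80, 1.21, 1.20 | 51.25%, 50% | hold, discontinue, counted | same |
| 0.8, 1.2, 1.3 | 50%, 62.5% | nothing on the first reading; the second is a fresh trigger | hold, discontinue, counted |
| 0.80, 1.19, 1.19 | 48.75%, 48.75% | nothing | nothing |

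The first three rows end at the same 50%, but the first is handled differently. Two participants like the first row at one dose level contribute 0 to the cohort stop as written and 2 with the aligned trigger, which would stop the cohort. The fourth row shows that the gap lasts only while the rise stays at exactly 50%.

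**2. Where exactly 50% can be reported.** Baseline × 1.5 must be a reportable value, so the baseline must be an even number of reporting units. The documents state neither the reporting precision nor a creatinine range, so both are assumed.

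| Assumed baselines | Reported to 0.1 | Reported to 0.01 |
|---|---|---|
| 0.6 to 1.2 | 4 of 7 | 31 of 61 |
| 0.5 to 1.2 | 4 of 8 | 36 of 71 |
| 0.5 to 1.3 | 4 of 9 | 41 of 81 |

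**3. First value that does trigger the hold**, at affected baselines from 0.6 to 1.2:

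- Reported to 0.1: 1.0/0.6 = +66.7%, 1.3/0.8 = +62.5%, 1.6/1.0 = +60.0%, 1.9/1.2 = +58.3%.
- Reported to 0.01: from 0.91/0.60 = +51.7% down to 1.81/1.20 = +50.8%.

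**4. Doses at stake in Part B.** Section 1.3, Table 3 schedules on-treatment safety blood on Days 4, 7, 10 and 14, with dosing on Days 1 to 14. Assume the result arrives after that day's dose.

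- Doses remaining: 14 − 4 = 10, 14 − 7 = 7, 14 − 10 = 4, 14 − 14 = 0.
- If the rise passes 50% at the next scheduled draw, counting that day's dose: 7 − 4 = 3, 10 − 7 = 3, 14 − 10 = 4.
- If creatinine is checked daily and passes 50% the next day: 0 doses if the result precedes that day's dose, 1 if it follows.

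The 10, 7 and 4 are ceilings. They are fully attributable to the wording only if the repeat is again exactly 50% and nobody stops dosing by judgment. If the repeat falls below 50%, the aligned rule would have withheld only the doses due before that repeat.

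**The case against.** The best reply is that this is a copy-edit at one point on the scale, overtaken by stronger rules. An exact 50% rise, absent another cause, is an important medical event, and Section 10.3.2 says of such events: "These events should usually be considered serious". Under Section 4.4 an SAE during active treatment pauses dosing for everyone. If it is drug-related or of unknown relationship, "dosing at the current dose level will be stopped, and further dose escalation will be terminated". One participant suffices there, against two in Section 10.6.2.3.

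Other layers also apply. Section 10.6.2.2 calls for prompt evaluation of suspected AKI, including creatinine, and adds: "Close daily observation of the participant and assessment of kidney function should be continued until the SCr elevations" and related urinalysis findings settle. Under Section 6.6, for consistent notable AEs or safety concerns attributed to drug, "continued dosing within the cohort will be temporarily halted and no participants will be dosed until full safety review can take place". Section 7.1 allows discontinuation for an AE or by physician decision, and Section 8 asks for immediate discussion of safety concerns with the sponsor. Table 20 and Section 8.3.5 prompt repeat tests, and Section 10.6.2.4 has a separate cystatin-C rule. In Part A there is one dose per period, and in Cohorts 1 and 2 the next dose is at least 5 days later, after new check-in laboratory tests.

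Much of this stands. The participant is not left without care, the SAE route can be stricter than the missing hold, and the exposure is mainly in Part B. The discontinuation step is also worded as *should*. What does not follow is that the gap is closed. Each route rests on suspicion, a seriousness or causality judgment, discretion, or another marker or threshold. None applies the 10.6.2.1 hold automatically at exactly 50%, and none adds the participant to the cohort count, which refers only to 10.6.2.1.

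**Conclusion.** The concern holds as a minor point: the trigger is wrong as written. A rise that is and stays exactly 50% falls outside the hold, the rule-based discontinuation and the cohort count, although the same protocol classes it as potential AKI when there is no other cause. Results below or above 50% are handled consistently.

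The conclusion rests on the literal wording alone and needs no numerical assumption. The size does: about half of the assumed baselines can produce an exact 50% value, but the documents give no basis for saying how often one would occur or persist. Screening also excludes an eGFR below 90 (exclusion criterion 11), which narrows the real range of baselines in a way not modelled here. With 0.01 mg/dL reporting the trigger moves by only about 1 to 2 percentage points; with 0.1 reporting it moves by about 8 to 17.

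**What to change.** In Protocol Section 10.6.2.1, change the hold trigger from >50% to ≥50%. The definition, hold and confirmation then agree, and Section 10.6.2.3 follows by reference without further edits. The cost is one symbol in the next amendment. Handling at 49% and at 51% does not change, and neither the schedule of assessments nor the SAP needs revision.

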10.6.2.2. Evaluation of Potential Cases of AKI

Participants suspected of having potential AKI should promptly (as soon as practically feasible, preferably within 24 hours of awareness) have an evaluation, which includes a detailed medical history, physical examination, and laboratory tests.

Laboratory tests include, at a minimum:

- Serum:
 - BUN, creatinine, sodium, potassium, chloride, bicarbonate, phosphorus, and calcium
 - Creatine kinase and cystatin-C
- Urine: Dipstick, microscopic examination, indices, and β-2-microglobulin.

Consider consultation with a nephrologist.

Close daily observation of the participant and assessment of kidney function should be continued until the SCr elevations and the associated abnormal UA results return to baseline or normalize.

10.6.2.3. Stopping Criteria for the Cohort

Further dosing with IMP will be stopped for the cohort if ≥ 2 healthy participants within a given dose level meet the criteria established in Section 10.6.2.1 and permanently discontinued IMP.

10.6.2.4. Stopping Criteria for Dose Escalation

Serum creatinine may be potentially impacted by OCT2, MATE1, and MATE2K transporter inhibition by test drugs. Serum cystatin-C, which is not affected by the above transporters, may be used to monitor renal function. If \geq 2 healthy participants within the same dosing level/cohort have a decline in eGFR cystatin-C \geq 25% from baseline using the CKD-EPI 2012 formula for cystatin-C (Inker et al, 2012), then dose escalation stops.

10.7. Appendix 7: Abbreviations

Abbreviation Definition

ACLS Advanced Cardiovascular Life Support

AE adverse event

AESI adverse event of special interest

AKI acute kidney injury

ALT alanine aminotransferase

APMP Abuse Potential Monitoring Plan

AST aspartate aminotransferase

AUC area under the concentration-time curve

BID twice daily

BUN blood urea nitrogen

C_{avg} average plasma concentration

CKD-EPI Chronic Kidney Disease Epidemiology Collaboration

C_{max} maximum plasma concentration

COVID-19 coronavirus disease-2019

CSR clinical study report

C-SSRS Columbia-Suicide Severity Rating Scale

CYP cytochrome P450

DAMGO [D-Ala2, N-MePhe4, Gly-ol] enkephalin

ECG electrocardiogram

eCRF electronic case report form

eGFR estimated glomerular filtration rate

EU European Union

F bioavailability

fa fraction absorbed

f_h fraction escaping hepatic metabolism

f_m fraction metabolized

FSH follicle stimulating-hormone

f_u fraction unbound

GCP Good Clinical Practice
HED human equivalent dose
ICF informed consent form

ICH International Council for Harmonisation

ID₅₀ dose required for 50% inhibition

Abbreviation Definition

IMP investigational medicinal product

KDIGO Kidney Disease: Improving Global Outcomes

IRB Institutional Review Board

K_i inhibition constantKOR kappa opioid receptorMAD multiple ascending dose

MATE multidrug and toxin extrusion protein

MDD major depressive disorder

MedDRA Medical Dictionary for Regulatory Activities

MOR mu opioid receptor

MTD maximum tolerated dose

NCI-CTCAE National Cancer Institute-Common Terminology Criteria for Adverse Events

NOAEL no observed adverse effect level

OCT organic cation transporter

PK pharmacokinetic(s)

QD once daily

QTcF QT interval corrected for heart rate using Fridericia's formula

SAD single ascending dose
SAE serious adverse event
SAP statistical analysis plan

SCr serum creatinine
SRT Safety Review Team

t_{1/2} apparent terminal half-life

 T_{max} time of maximum observed concentration

UA urinalysis

UGT UDP-glucuronosyltransferase

ULN upper limit of normal

10.8. Appendix 8: Protocol Amendment History

The Protocol Amendment Summary of Changes Table for the current amendment is located directly before the Table of Contents.

Amendment: Protocol Version 2.0 (16 Sep 2021)

Section # and Name	Description of Change	Brief Rationale
1.1 Synopsis 3 Objectives and Endpoints	Added AEs potentially related to abuse to TEAE endpoint (SAD and MAD tables)	To align with addition of such events to Section 8.4.6 (Adverse Events of Special Interest)
	Added clarification that the following PK endpoints are for Day 14: CL/F; V _Z /F; PTR; Rac, C _{max} ; Rac, AUC; t _{1/2} ; and renal clearance (MAD table)	Data required for calculation of these endpoints are only collected at steady state
1.1 Synopsis 4.2 Scientific Rationale for Trial Design	Deletion of parallel-group language (MAD)	Internal consistency about sequential dosing of cohorts
1.2 Schema 4.1.1 Single Ascending Dose - Part A	Figure 1 and Table 6: Revised CVL-354 dosing paradigms for Cohort 2	To align with proposed doses as presented in Table 7
1.2 Schema	Figure 1: Randomization symbol (R) moved from beginning of Treatment Phase to text boxes for each cohort	To reflect randomization to sequence rather than to cohort
	Figure 1, Figure 2: Changed text boxes for cohorts in Treatment Phase from parallel to staggered	To more accurately depict sequential dosing of cohorts
1.3 Schedule of Assessments	Table 1 (SAD), Table 2 (MAD): Revised tables to indicate that medical occurrences before the start of IMP dosing but after obtaining informed consent will be recorded as medical and/or psychiatric history and that AEs will be recorded from the first dose of IMP	To clarify recording timeframes relative to informed consent and first dose of IMP, including for replacement participants
	SAD: Changed limited physical and neurological examinations to full examinations at each Check-out (or ET) MAD: Changed limited physical and neurological examinations to full examinations on Day 7 and Day 17/ET	To provide additional opportunities to potentially identify AEs related to the gastrointestinal or central nervous systems, reflecting the addition of such events to Section 8.4.6 (Adverse Events of Special Interest)

Section # and Name	Description of Change	Brief Rationale
	Table 1 (SAD): Changed "Check-in Period 1" to "Initial Check-in" and "Check-in Periods 2-4" to "Subsequent Check-ins"	To clarify procedures for replacement participants, including recording of medical and/or psychiatric history and AEs
	Moved Randomization from Initial Check-in (Day -1) to Predose and added footnote that it is applicable to Period 1 only	To allow for completion of all assessments required for determination of eligibility
	Table 2 (MAD):	
	Day 2: Added C-SSRS	To obtain additional data for monitoring of suicidal ideation and behavior
	Day 1: Removed blood sample for safety laboratory Day 10: Added footnote to respiratory rate and temperature	To correct errors in the previous version of the protocol
	Table 2, Table 3 (MAD): Revised tables to reflect addition of on Day 1	
4.2 Scientific Rationale for Trial Design	Added a statement referring to development of an APMP for the trial	To enhance understanding of the safety profile of CVL-354 and to provide guidance to site personnel for identification and reporting of AEs potentially related to abuse
4.4 Guidance for Dose Escalation/Stopping Rules	Revised and reorganized content to summarize potential SRT actions following review of data and to further define criteria for which the SRT may consider stopping further dose escalation	To clarify actions and more specifically define AEs or other abnormalities that would be considered in the determination of MTD
	Added a paragraph that summarizes the process and the potential impact on dose escalation if an SAE were to occur during active treatment	

Section # and Name	Description of Change	Brief Rationale
5.2 Exclusion Criteria	Exclusion Criterion #11: Added "at Screening" to criterion for estimated glomerular filtration rate	To clarify timeframe for determination of eligibility
	Exclusion Criterion #13: Moved symptomatic orthostatic dizziness text to a separate bullet within the criterion	To separate the text from the bullet that defines orthostatic hypotension
5.2 Exclusion Criteria	Exclusion Criterion #16: Increased duration of abstention from 48 hours prior to Day -1 to 7 days prior to Day -1	To ensure minimal to no interaction with IMP
5.3.1 Meals and Dietary Restrictions	Increased duration of abstention from 48 hours prior to Day -1 to 7 days prior to Day -1	
5.4 Screen Failures	Deleted language about SAEs	To align with changes to language about AE recording starting from first dose of IMP
6.3.1 Participant Assignment to Treatment	Revised language to specify that replacement participants in Part A (SAD) will be randomized to the same sequence and replacement participants in Part B (MAD) will be randomized to the same treatment	To reflect differences in trial design between SAD (randomization to sequence) and MAD (randomization to treatment)
6.3.2 Blinding	Added instructions in the event of emergency unblinding	To clarify unblinding procedures in case of emergency
8.4.1 Time Period and Frequency for Collecting AE and SAE/AESI Information	Clarified that AEs will be recorded from the first dose of IMP and medical occurrences that begin before the start of IMP dosing but after obtaining informed consent will be recorded as medical and/or psychiatric history	To confirm timeframes for medical history and AE recording relative to informed consent and first dose of IMP
8.4.6 Adverse Events of Special Interest	Detailed narratives, rather than brief narratives, will be written for any participant who develops an AESI Revised AESI definitions as follows: Added Grade 2 moderate AEs related to the gastrointestinal system Added Grade 2 moderate AEs related to the central nervous system Added AEs potentially related to abuse (followed by summary of key aspects of the APMP)	To enhance understanding of the safety profile of CVL-354 and to provide guidance to site personnel for identification and reporting of AEs potentially related to abuse
8.6 Pharmacokinetics	Added a sentence regarding possible retention of samples for evaluation of bioanalytical methods and metabolites for up to 1 year after CSR completion	Updated as per sponsor's policy on PK sample management

Section # and Name	Description of Change	Brief Rationale
9.4.2 Safety Analyses	Added AEs potentially related to abuse	To align with addition of such events to Section 8.4.6 (Adverse Events of Special Interest)
10.3.3 Recording and Follow- Up of AEs and/or SAEs/AESIs	Deleted the following language:that are identified at any time during the trialhaving been identified throughout the trial	To align with changes to language about AE recording starting from first dose of IMP
10.3.3 Recording and Follow- Up of AEs and/or SAEs/AESIs 10.3.4 Reporting of SAEs and AESIs	Addition of "AESI" or "AESIs" to section headings and throughout tables within the respective sections	To correct inadvertent omission in the previous version of the protocol
11 REFERENCES	Added new reference: FDA Guidance for Industry, 2017	To reflect inclusion of citation in content regarding abuse potential monitoring added to Section 8.4.6 (Adverse Events of Special Interest)
Overall	General grammatical and wording corrections/clarifications made throughout protocol	To correct minor errors from the previous version of the protocol

Abbreviations: AE=adverse event; AESI=adverse event of special interest; APMP=Abuse Potential Monitoring Plan; AUC=area under the concentration-time curve; CL/F=apparent clearance of drug from plasma; C_{max} =maximum plasma concentration; CSR=clinical study report; C-SSRS=Columbia-Suicide Severity Rating Scale; ; ET=Early Termination; IMP=investigational medicinal product; MAD=multiple ascending dose; MTD=maximum tolerated dose; PK=pharmacokinetic; PTR=peak-to-trough ratio; R=randomization; Rac=accumulation ratio; SAD=single ascending dose; SAE=serious adverse event; SRT=Safety Review Team; $t_{1/2}$ = apparent terminal half-life; TEAE=treatment-emergent adverse event; V_Z /F= apparent volume of distribution during terminal phase.

